10.5 ACTIVATOR II SUPPLY

For all the study subjects, Activator II will be obtained from the site consignment supplied by JJSV prior to study initiation. One Activator II will be used on each eye of a subject. Unused back-up Activators are to be returned to the site consignment. At the completion of study enrollment, any remaining Activator II devices will be shipped back to JJSV following the final JJSV monitoring visit. At all times, the storage, access and use of all the consignment Activators must be controlled.

The IOLs for all the study subjects will be obtained from the site's own inventory.

10.6 POSTOPERATIVE PROCEDURES

Postoperatively, subjects will be examined according to the schedule in Section 10.2, Visit Schedule. The most recently operated eye will be evaluated at the 1-day and 1-week visits per site practice standard of care. Both eyes will be evaluated for all the subjects at the 1-month and 3-month visits. For the subjects in Control group, both eyes will receive crossover LipiFlow treatment within 0 - 7 days after the 3-month postoperative visit, and will be evaluated at the 4-month visit.

To maintain consistency throughout the study, it is recommended that a single individual (study technician or coordinator designated by the investigator) conduct all postoperative study-related vision testing. In addition, a back-up person should also be designated and trained.

NOTE 1: No additional refractive procedures are to be performed during the operative or postoperative study period (e.g., Limbal-Relaxing Incisions (LRIs), PRK, LASIK or LASEK).

NOTE 2: If the subject chooses to wear contact lenses after the cataract surgeries, they must be removed prior to any postoperative visits and prior to any LipiFlow treatment. The subject may resume contact lens wear one hour after completion of treatment or per site standard of practice.

NOTE 3: If the subject is implanted with a TECNIS Symfony IOL only in the first eye, the subject will be followed for monocular testing only until study exit for that first eye. The fellow eye will be considered exited as of the second operative date. Both eyes may still receive the LipiFlow treatment if the subject was randomized to the Control group.

POSTOPERATIVE EXAMINATION PROCEDURES

Postoperative examinations will be conducted 1 and 3 months after second-eye cataract surgery for all subjects, and at 4 months for Control group subjects only. General descriptions and requirements of the various tests are provided in **Appendix D**. The postoperative case report form (CRF) will collect the following information, although not all information is required at every visit (see **Appendix B**):

MANIFEST REFRACTION AND REFRACTION ADJUSTMENTS

Postoperative study manifest refractions are to be performed using the M&S System at a distance of 4.0 meters. Manifest refraction (MR) is to be performed using the Maximum Plus refraction method as detailed in **Appendix M**.

Because 4.0 meters is not optical infinity, refraction adjustments are necessary to ensure proper vision testing, taking into account test distance and refraction distance. **Appendix N** lists the refraction adjustments required for the various vision tests using the BCDVA refraction.

DISTANCE VISUAL ACUITY TEST

Monocular and binocular uncorrected and distance corrected visual acuities will be measured postoperatively under photopic lighting conditions (85 cd/m², 80–110 cd/m² acceptable) using the M&S System at a test distance of 4.0 meters. For eyes unable to achieve a postoperative BCDVA of Snellen 20/40 (i.e., LogMAR 0.3, number of letters correct 70), a reason must be specified. Instructions for using the M&S System are detailed in **Appendix O**, and for distance visual acuity in **Appendix P**.

The following distance visual acuity measurements are to be performed per the visit schedule in **Appendix B**:

Test	Test Distance	Illumination	Type of Testing	Refraction Adjustment
UCDVA	4 m	Photopic (85 cd/m ²)	Monocular, Binocular	+0.25 D adjustment only
BCDVA	4 m	Photopic (85 cd/m ²)	Monocular, Binocular	No adjustment; ETDRS Rx only

INTERMEDIATE VISUAL ACUITY TEST

Binocular uncorrected intermediate visual acuity will be measured under photopic conditions (85 cd/m², 80–110 cd/m² acceptable) using the M&S System at a test distance of 66 cm. Instructions for using the M&S System are detailed in **Appendix O** and for intermediate testing in **Appendix Q**.

The following intermediate visual acuity measurements are to be performed per the visit schedule in **Appendix B**:

Test	Test Distance	Illumination	Type of Testing	Refraction Adjustment
UCIVA	66 cm	Photopic (85 cd/m ²)	Binocular	No adjustment

NEAR VISUAL ACUITY TEST

Binocular uncorrected near visual acuity will be measured under photopic conditions (85 cd/m², 80-110 cd/m² acceptable) using the M&S System at a test distance of 40 cm.

Instructions for using the M&S System detailed in Appendix) and for near testing in **Appendix R**.

The following near visual acuity measurements are to be performed per the visit schedule in **Appendix B**:

Test	Test Distance	Illumination	Type of Testing	Refraction Adjustment
UCNVA	40 cm	Photopic (85 cd/m ²)	Binocular	No adjustment

CONTRAST ACUITY TESTING

Binocular, photopic, 10% low contrast acuity and 20/40 contrast threshold tests will be measured using the M&S System. Detailed instructions for contrast acuity testing are provided in **Appendix S**.

BIOMICROSCOPIC SLIT-LAMP EXAM

A biomicroscopic slit-lamp exam must be performed at each postoperative visit to determine the presence or absence of any medical or lens findings, complications or adverse events. IOL decentration and tilt are to be determined subjectively. The center of the lens relative to the pupil can be used to determine IOL decentration. The diffractive rings of Symfony lens can be used as a guide to locate the center of the IOL. Note that the pupil center may not always be aligned with the visual axis of the eye; therefore, the investigator should consider deviations in pupil center from visual axis when reporting IOL decentration.

ND:YAG CAPSULOTOMY

If an Nd:YAG capsulotomy is necessary, it is recommended that the procedure be performed after study completion.

MEIBOMIAN GLAND ASSESSMENT

Meibomian glands assessment is to be measured at the designated postoperative visits. The method of the assessment is described in **Appendix G**.

FUNDUS EXAM

A dilated fundus exam will be done preoperatively and may be performed postoperatively at the investigator's discretion. Examinations may be done dilated with ophthalmoscopy or undilated with any imaging system that allows for undilated views of peripheral retina (e.g., Optomap). The same fundus exam method that was used for preoperatively should be used postoperatively if the exam is performed.

MEIBOMIAN GLAND IMAGING (LIPISCAN/LIPIVIEW II)

Meibomian gland imaging will be captured through LipiScan or LipiView II at the designated visits, to capture Meibomian gland images of both eyes and grade eyelids, as shown in **Appendix I**. Refer to the LipiView Interferometer and LipiScan Instructions for Use for detailed instructions on the device operation. For subjects in Control group, both eyes will be measured at 4-month visit as well. It is recommended that the same methods be used for all study subjects at the site for the duration of the study.

**STANDARD PATIENT EVALUATION OF EYE DRYNESS (SPEED)
QUESTIONNAIRE**

The SPEED questionnaire will be administered at the beginning of any designated visits, prior to any visual acuity testing.

**OCULAR / VISUAL SYMPTOMS ASSESSMENT (NON-DIRECTED;
SPONTANEOUS)**

The subjective ocular / visual symptoms are to be assessed at the designated visits by asking "Are you having any difficulties with your eyes/vision?" Subjects should not be prompted for specific responses; however, if a subject complains of halos, glare or starbursts, the severity should be determined (mild, moderate or severe).

PRVSQ QUESTIONNAIRE

The PRVSQ questionnaire is to be assessed at the designated visits. Subjects will be prompted for specific responses, including halos, night glare or starbursts.

MEDICATIONS

Postoperative medications should be used as is customary for each investigator and recorded in the source document for each subject. Medications will be recorded on each postoperative case report form as applicable.

ADVERSE EVENTS

Subjects should be assessed at each visit for occurrence of and/or change in status of any adverse events, particularly serious and/or device-related adverse events.

See Section 11.0, Adverse Events, for further information.

ADDITIONAL PROCEDURES AT DESIGNATED POSTOPERATIVE VISIT(S):

- Eyelid margin evaluation for each eye
- TBUT for each eye
- Ocular surface staining for each eye
- Ocular and systemic medications

Crossover LipiFlow Treatment (Only for Control Group)

The crossover LipiFlow treatment is only applicable to and required for the subjects in the Control group. It will be performed on the Control group subjects on the same day or within 1 week of the 3-month postoperative visit, after all study examination procedures are completed. If the subject has an active ocular adverse event or other contraindications to LipiFlow treatment, the LipiFlow treatment should not be performed at this visit.

The LipiFlow treatment should be performed per the LipiFlow System Instructions for Use.

10.7 EXIT OF SUBJECTS

An Exit Case Report Form will be completed for all subjects, either when they complete the study or if they exit early.

It is the responsibility of the investigator to provide complete follow-up data to JJSV for each subject, and every attempt should be made to gather that complete follow-up data for all subjects enrolled as missing data can have a negative effect on the study results. Patients who will be traveling, relocating or otherwise unavailable for postoperative follow-up visits should not be chosen for this clinical study.

A subject will be considered a “screen failure” if he/she does not meet the inclusion/exclusion criteria or if consent is withdrawn prior to randomization.

A subject will be considered “discontinued prior to treatment” if the subject is randomized but does not undergo bilateral LipiFlow treatment (study group) or receive a Symfony lens for various reasons including: the planned implant being aborted due to surgical complications, the subject withdrawing consent prior to treatment, or the subject died prior to treatment. If a subject receives at least one Symfony lens, he/she is to be followed according to the protocol.

A subject will be “discontinued” from the study if one study lens (if implanted unilaterally) or both study lenses (if implanted bilaterally) are removed or if the subject dies.

Subjects will be considered “lost-to-follow-up” from the study only if irretrievably lost for unavoidable reasons such as: subject moved/unable to locate, subject uncooperative/refuses further study participation, subject ill/unable to travel. In the event of subject relocation, efforts must be made by the investigator to secure follow-up information (i.e., slit-lamp findings and general visual acuity, etc.) from the subject’s new physician.

If a subject is exited early from the study, the investigator will send an Exit Case Report Form to JJSV indicating the reason for study exit. In the event of a lens removal or other serious adverse event, the subject may be exited from the study; however, efforts must be made by the investigator to follow the subject until resolution of the adverse event.

Following study completion or early exit, all study subjects are to be instructed to undergo regular eye examinations at least yearly and also to return to their doctor if any eye complications are experienced in the interim.

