As the Informed Consent Form is signed at the beginning of the preoperative visit, some subjects may not qualify after study-specific testing is performed. Subjects will be considered screen-failures if they do not qualify or if they qualify but decide not to proceed with surgery. These subjects will be exited from the study.

Screening and Baseline

Following the informed consent process, the Investigator or designee will perform the screening and baseline exam procedures and evaluate the subject conditions that affect study eligibility, as listed in Sections 8.1 and 8.2. The screening and baseline exam may be ended prior to completion if the Investigator or designee determines that the subject does not meet one or more of the eligibility criteria. The subject must meet all the study inclusion and exclusion criteria based on testing conducted at the Visit #1.

Besides Medical and Ocular History, the screening and baseline exam to be performed for each eye includes:

MEDICAL AND OCULAR HISTORY

To determine the presence of any systemic or ophthalmic factors that may affect the subject's eligibility based on the study inclusion and exclusion criteria in Sections 8.1 and 8.2, the Investigator or designee obtain the subject's medical and ophthalmic history at the visit, including assessment of:

- 1) demographic information (age, gender, race/ethnicity);
- 2) systemic conditions and concomitant systemic medications that may cause dry eye;
- 3) ophthalmic conditions and medications, including last use of medications for MGD or dry eye and dosage and frequency of pre-existing use of OTC products;
- 4) history of contact lens wear (must be removed prior to examination and treatment);
- 5) history of ocular surgery, ocular injury, ocular infection, ocular inflammation, ocular allergy, eyelid abnormality, or ocular surface abnormality;
- 6) recent participation in another ophthalmic clinical trial.

BIOMICROSCOPIC SLIT-LAMP EXAM

A biomicroscopic slit-lamp exam must be performed at the study visit to determine if the subject meets inclusion/exclusion criteria. The Investigator or designee evaluates the eyelids, palpebral and bulbar conjunctiva, cornea, anterior chamber, iris and lens using a slit lamp biomicroscope. The Investigator or designee everts the upper eyelid to evaluate the upper palpebral conjunctiva. The Investigator or designee assesses the findings for the presence of any adverse events.

MEIBOMIAN GLAND ASSESSMENT

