If the LipiFlow treatment is performed on the same day as Preoperative Visit #1, the medical/ophthalmic history and slit lamp evaluation do not need to be repeated before treatment. In this case, the Investigator must review the baseline history and slit lamp exam information prior to treatment to ensure no contraindication to LipiFlow treatment is present. If the LipiFlow treatment visit is performed on a different day from Preoperative visit #1, the Investigator or designee documents any changes to medical/ophthalmic history and performs a slit lamp evaluation to determine if an ocular adverse event is present prior to treatment. If the subject has an active ocular adverse event, the LipiFlow treatment should not be performed at this visit.

The Investigator or designee cleans the lid margin (**Appendix E**) and then performs treatment with the LipiFlow system per the LipiFlow System Instructions for Use. The Investigator documents any problems with the LipiFlow system during treatment. The Sponsor will investigate any reported problem with the LipiFlow system.

The Investigator or designee performs slit-lamp evaluation after LipiFlow treatment to check for any adverse events. At the completion of the exam, the subject is instructed on how to perform blinking exercises (**Appendix F**) for 1 month after treatment to facilitate the flow of oils from the meibomian glands into the tear film. The subject is advised to return for Pre-Operative Visit #2, which must be scheduled 2 - 4 weeks after the LipiFlow treatment.

At the completion of Preoperative Visit #1, the subject is reminded not to use any MGD or dry eye prescription medications or other treatments during the study (except for pre-existing OTC artificial tears, ocular lubricants, ointments, emollients or ω-3 dietary supplements). The dosage and frequency of any pre-existing use of OTC products upon study entry must be documented in the subject's medical record and in the study case report forms. Except for LipiFlow treatment, no other MGD or dry eye treatment is prescribed or administered to subjects throughout the study.

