20.5 SAMPLE SIZE CALCULATIONS

The sample size determination is based on the primary endpoint of uncorrected distance visual acuity (UCDVA). There is 90% power to detect a 1-line or greater difference in mean UCDVA between the treatment and control groups with 55 subjects in each group. This assumes one-sided two-sample t-test with an alpha of 0.05 and standard deviation of 1.6 lines. Adding 20% screen failure/drop-out rate will require enrolling 69 subjects per group.

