#### 2 ANALYSIS POPULATIONS

#### 2.1 ANALYSIS POPULATIONS

The primary analysis population will be all eyes that are randomized for the precision of biometric measurements, and all eyes that are randomized and implanted for all other analyses. Mean change in total Meibomian gland score will be compared between study group eyes and control group eyes at 1 month postoperatively. All other key study endpoints will be evaluated at 3 months postoperatively. Additional endpoints will be evaluated at 1 month and 3 months postoperatively for the study group and control group and 4 months postoperatively for crossover control group only. Missing data will not be imputed.

Since both eyes of the same subject will be randomized into the same group, eye-specific measurements of same subject are clustered and likely to be positively correlated. As a subset analysis, right and left eyes of subjects will be analyzed for the key eye-specific study endpoints separately to assess for any differences by eye. Demographics/enrollment/accountability data and binocular data will be reported for all randomized subjects with study IOLs successfully implanted.

Version 1.0 1 SAP/DRYE-102-SELF

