#### 5 SAMPLE SIZE CALCULATIONS

The sample size determination is based on the primary endpoint of uncorrected distance visual acuity (UCDVA). There is over 90% power to detect a 1-line or greater difference in mean UCDVA between the treatment and control groups with 55 subjects in each group. This assumes one-sided two-sample t-test with an alpha of 0.05 and standard deviation of 1.6 lines. Adding 20% screen failure/drop-out rate will require enrolling 69 subjects per group.

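### Protocol Section 10.7 gives only the Study arm an exit class for missed LipiFlow and does not say whether those subjects continue to surgery and analysis; if they leave, the loss is one-sided.

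*Protocol*

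**What the plan says.** **Exit class.** Protocol 10.7 defines *discontinued prior to treatment* as a subject "randomized but does not undergo bilateral LipiFlow treatment (study group) or receive a Symfony lens". The LipiFlow limb names the Study group; the Symfony limb covers both arms. The last sentence of that paragraph says that a subject with at least one Symfony lens is followed under the protocol, and sets no LipiFlow condition.

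**Reasons for missing LipiFlow.** Preoperative LipiFlow is due on the day of Preoperative Visit #1 or in the following week. For treatment on a later day, Protocol 10.3 requires a slit-lamp check and adds: "If the subject has an active ocular adverse event, the LipiFlow treatment should not be performed at this visit". It does not say what follows if that week passes untreated.

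**Analysis sets.** SAP 2.1, like Protocol 20.1, uses all randomized eyes for biometric precision and "all eyes that are randomized and implanted for all other analyses". Missing data are not imputed. SAP 3.1 counts discontinued subjects among the missing.

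**Visit #2.** Protocol 10.2, 10.4 and Appendix B time the Study arm's second preoperative visit from LipiFlow, and the Control arm's from Visit #1.

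**Screen failure.** The consent text in Protocol 10.3 also counts subjects as screen failures "if they qualify but decide not to proceed with surgery". Section 10.7 confines the term to ineligible subjects and to consent withdrawn before randomization.

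**The concern.** The Study arm has a checkpoint between randomization and surgery that Control does not have. A Control subject who misses the crossover treatment does so after 3-month UCDVA has been measured, and Protocol 10.6 attaches no exit label to that.

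A site could reasonably read the Section 10.7 label as an instruction to exit the subject, since it stands in the exit section beside the definitions of discontinued and lost to follow-up. A subject exited before surgery is not implanted in the study, so the sentence that protects implanted subjects never applies. The eyes then drop out of the UCDVA set in one arm only. For biometry the eyes stay in the set by definition but have no Visit #2 value. Even a site that wants to keep the subject has no Visit #2 window to use.

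If the reason for missing treatment is related to later acuity, as an active ocular adverse event might be, the loss is selective. The trial is open-label, so nothing in the design would stop sites from applying the rule differently.

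**Working it through.** **1. The plan's own figures.** "The sample size determination is based on the primary endpoint of uncorrected distance visual acuity (UCDVA"), with 55 subjects per group, SD 1.6 lines, a 1-line difference, one-sided alpha 0.05 and 20% loss.

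- Inflation: 55 / (1 − 0.20) = 68.75, so 69 per group. This reproduces.
- Noncentrality at 55 per group: 1 / (1.6 × √(2/55)) = 3.28. One-sided power is 94.7% by noncentral t (94.9% normal).
- The Protocol says "There is 90% power to detect a 1-line or greater difference in mean UCDVA". A two-sided 0.05 test gives 90.1%. For the stated one-sided test the Protocol's figure is conservative, and the SAP's wording, "There is over 90% power to detect a 1-line or greater difference in mean UCDVA", is correct. The difference does not affect this point.

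**2. Where a Study subject without LipiFlow ends up.**

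| Course after the missed treatment | Follow-up | UCDVA set | Biometry value at Visit #2 |
|---|---|---|---|
| Goes on to in-study implantation | Yes, by the follow-up sentence in 10.7 | Included | No defined visit window |
| Label applied as an exit before Visit #2 | None | Absent, not imputed | None |
| Label applied as an exit after Visit #2, before surgery | None | Absent, not imputed | Possible, but no defined window |

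The text does not choose between these rows. In Control only the absence of a Symfony lens triggers the class.

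**3. What exits would do to UCDVA.** Let *f* be the share of the Study arm that exits and *d* the number of lines by which those subjects' 3-month UCDVA would have been worse than the mean of the whole Study arm. The mean of those remaining moves by

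bias = *f* × *d* / (1 − *f*).

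The documents give neither *f* nor *d*; both are assumed. The error rate is that of the one-sided t-test with SD 1.6, 55 Control subjects, 55 × (1 − *f*) Study subjects (52 at 5%, 50 at 10%), no true effect and one value per subject.

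| *f* | *d* (lines) | Bias (lines) | One-sided error |
|---|---|---|---|
| 5% | 0 | 0 | 5.0% |
| 5% | 0.8 | 0.05 × 0.8 / 0.95 = 0.042 | 6.6% |
| 5% | 1.6 | 0.05 × 1.6 / 0.95 = 0.084 | 8.5% |
| 10% | 0 | 0 | 5.0% |
| 10% | 0.8 | 0.10 × 0.8 / 0.90 = 0.089 | 8.7% |
| 10% | 1.6 | 0.10 × 1.6 / 0.90 = 0.178 | 14.0% |

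Five to ten percent of 69 is about 3 to 7 subjects. At *f* = 2% and *d* = 0.8 the error is 5.6%. If exit is unrelated to acuity there is no bias, and power for 1 line is 94.1% (5% lost) or 93.7% (10% lost).

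**4. Cost of keeping them.** If untreated Study subjects are retained and have no effect at all, a 1-line effect is diluted to (1 − *f*) lines. At 55 per arm, one-sided power is then 93.9% (2% untreated), 92.6% (5%), 90.1% (10%) and 86.9% (15%).

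**The case against.** The strongest reply is that the documents assign a label and never say that it ends participation before surgery. One of the examples listed under it, an implant aborted through surgical complications, can only arise at surgery, so the class is not inherently a preoperative exit. Section 10.7 also asks for complete follow-up of all enrolled subjects, and Section 10.3 counts everyone randomized as enrolled. No text removes an implanted Study eye from the UCDVA analysis because LipiFlow was missed.

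That stands. A reader might infer that the UCDVA comparison is already no longer as randomized; the documents do not support this, because loss occurs only if the label is applied as an exit. A reader might also infer that the loss favours LipiFlow. That needs the exiting subjects to have had worse acuity than their arm, which is not shown. The rule on adverse events withholds treatment at that visit only, active ocular infection and inflammation are excluded at baseline, and the treatment window is about a week, so few subjects may be affected.

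Two further points are fair. The screen-failure mismatch applies to both arms, so it concerns subject accounting and does not add to the asymmetry. And conditioning on implantation is itself post-randomization, but the rule is the same in both arms.

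The gap remains: the follow-up sentence helps only those who reach in-study surgery, and nothing says that a labelled subject does.

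**Conclusion.** The point holds as an unresolved conflict. Section 10.7 creates a Study-only class whose consequences are not stated, and it must be reconciled with its own follow-up sentence and with Protocol 20.1 and SAP 2.1. Read as an exit, it permits a one-sided loss after randomization that could affect the UCDVA and biometry comparisons. Read as a label only, it does UCDVA no harm, but Visit #2 is still undefined for these subjects.

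Size and direction cannot be derived from the documents. The range of 5% to about 14% for the one-sided error rests wholly on the assumed 5-10% exiting and 0 to 1.6 lines, and on one value per subject where the plan analyses eyes. It shows what the wording allows and is not an estimate of bias. The change is worth making because it is cheap and has to be made before subjects are lost.

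**What to change.** 1. In Protocol 10.7, limit *discontinued prior to treatment* to subjects who receive no Symfony lens, in both arms.
2. State there, and in Protocol 20.1 and SAP 2.1, that Study subjects without bilateral LipiFlow remain in the study, attend Visit #2 and the postoperative visits, and are analysed in their assigned arm. Report the number who missed LipiFlow, with reasons.
3. In Protocol 10.2, 10.4 and Appendix B, give these subjects a Visit #2 window. Timing it from Visit #1, as in Control, would serve. This concerns assessment only and leaves open whether or when LipiFlow is given.
4. Align the consent text in Protocol 10.3 with Section 10.7, so that anyone leaving after randomization is counted as discontinued and not as a screen failure.

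The cost is a handful of wording changes across the two documents and continued follow-up of probably few subjects. The statistical price is the slight dilution shown in the working. No larger sample is needed up to about 10% untreated; at 15% power falls to about 87%.
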